## 7. EXPERIMENTAL TECHNIQUES AND METHODS

This will be a single center, with no randomization or blinding, study design in 30 healthy adult subjects, age 18-70 years. Based on prior experience approximately 30 subjects will be enrolled to ensure 20 subjects complete the study.

Skin response to the test product and both positive and negative controls will be evaluated and measured by an allergist. If the measured diameter is  $\geq 3$ mm in response to the test product with expected reactions to both the positive and negative controls, the site will be considered a positive allergen.

Initial reading will take place after 15 minutes looking for the presence or absence of a wheal and flare at all three sites and measuring the diameter of both the wheal and flare if present. The wheal at the positive control must exceed a wheal at the negative control by 3 mm. A second reading is conducted about 6 hours after the SPT administration and similar measurements are taken. The subjects return to the office 1-2 days after the initial administration for a third test reading and measurements. A positive reaction is present when there is a measurable wheal of  $>3$  mm. Small wheals are confirmed by palpation. The skin prick reaction is quantified by measuring the mean diameter of the wheal, using a ruler marked in mm. If the result is a circular wheal, one measurement of the diameter (in mm) is sufficient; if ovoid or irregular, two diameters are measured (smallest and largest) and the numbers are added and divided by 2 (mean diameter). A flare alone is measured but is not of any clinical significance. The flare, area of erythema, may also be recorded by the same method.

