## **14. STATISTICAL RATIONALE AND DATA REPORTING**

Evaluation of results consists of only one physiological measure (that of wheal/flare) measured at 3 time points: T1=15 minutes after SPT, T2=6hr after SPT and T3=24-48 hrs. after SPT. Our power analysis calculation indicates at a confidence level of 99% and confidence interval of 1.35, we will need a sample size of n=20. No statistical analysis will be performed. No significant effect or interaction effects are anticipated hence the small sample size. Skin responses to the test product and controls for each subject will be presented in a table in the final report.

Product reporting for skin sensitization will be based on statistically significant positive scores at each interval. Any subject that has erythema present in the negative control eliciting an allergic response will be included as long as the wheal diameter of the positive control exceeds the wheal size of the negative control by at least 3mm. This is to account for individuals who have sensitive skin. This data will be noted in the clinical findings.

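### Section 14 rests the product conclusion on significant scores at each reading, with no analysis planned and no summary of how many subjects reacted at any reading

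*Combined protocol and SAP*

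**What the plan says.** Section 2 asks about the product's potential to sensitize human subjects. Section 7 defines positivity for a site: if the product wheal is large enough and both controls behave as expected, "the site will be considered a positive allergen". That sentence names no reading and gives no rule for combining several. Each subject has one product site, read repeatedly.

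Section 14 describes a single measure, "measured at 3 time points: T1=15 minutes after SPT, T2=6hr after SPT and T3=24-48 hrs. after SPT". It then states "No statistical analysis will be performed" and promises a listing: "Skin responses to the test product and controls for each subject will be presented in a table in the final report". Its second paragraph gives the only stated basis for the product conclusion: "Product reporting for skin sensitization will be based on statistically significant positive scores at each interval".

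Two other provisions bear on the denominator. Sections 7, 9.6 and 14 require the positive-control wheal to exceed the negative-control wheal by 3 mm. Section 10 leaves a discontinued subject's data out of the analysis unless the discontinuation was related to the product.

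**The concern.** There are two faults in one sentence. It calls for statistical significance in a plan that has no test, comparator, significance level or analysis. Removing the word *significant* would leave the second fault: the conclusion would rest on three separate tallies, one per reading, and no result per person.

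The objective concerns people, and in a study of 20 to 30 subjects the natural headline is how many of them reacted. Three interval tallies do not determine that number. They can make it look smaller when the positives at different readings belong to different subjects. Without a rule set in advance, whoever writes the report decides how to combine the readings after seeing them, in a study that Section 7 describes as neither randomized nor blinded.

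**Working it through.** **1. The plan's own figure.** Section 14 says "Our power analysis calculation indicates" that "at a confidence level of 99% and confidence interval of 1.35, we will need a sample size of n=20". No standard deviation is given, nor a unit for 1.35, nor whether it is a half-width or a full width. For the precision of a mean, n = (z × SD / E)², with z = 2.576 at 99% two-sided.

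- E = 1.35 (half-width): n = 20 needs SD = 1.35 × √20 / 2.576 = 2.34. An SD of 1 to 3 gives n from 4 to 33.
- E = 0.675 (1.35 as full width): n = 20 needs SD = 0.675 × √20 / 2.576 = 1.17. An SD of 1 to 3 gives n from 15 to 132.

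The figure therefore cannot be confirmed. The present point does not depend on it. I use 20 only as a denominator, because Section 7 says "approximately 30 subjects will be enrolled to ensure 20 subjects complete the study".

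**2. The passages side by side.** Section 7 defines a positive site, and Section 14 refers to positive scores by interval and lists responses by subject. None of them says that a subject counts as positive if positive at any reading, or plans a count or proportion of such subjects.

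**3. What interval counts imply about people.** Let c1, c2 and c3 be the numbers positive at T1, T2 and T3 among the same n subjects, and R the number positive at least once. Then

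max(c1, c2, c3) ≤ R ≤ min(n, c1 + c2 + c3).

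The lower bound is reached when the positives at every reading fall within one group of people, the upper when no subject is positive twice. If everyone has all three readings, no interval rate can exceed R/n.

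**4. Illustrative counts, n = 20.** The limits are exact (Clopper-Pearson) 95%: lower = Beta(0.025; x, n − x + 1), upper = Beta(0.975; x + 1, n − x).

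| Positives on each line | Each line shows | Fewest reactors | Most reactors |
|---|---|---|---|
| 1 | 1/20 = 5% | 1/20 = 5% (0.1% to 24.9%) | 3/20 = 15% (3.2% to 37.9%) |
| 2 | 2/20 = 10% | 2/20 = 10% (1.2% to 31.7%) | 6/20 = 30% (11.9% to 54.3%) |

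Identical interval lines thus fit up to a threefold difference in the share of subjects who reacted. With no positives at all, both presentations give 0/20 (0% to 16.8%).

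**5. The denominator.** An any-reading rate depends on who is counted, and it can move either way:

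- One reactor among 20 completers is 1/20 = 5.0%. If 30 subjects had valid controls and at least one reading, and there were no further reactors, the rate would be 1/30 = 3.3%.
- Suppose 20 completers show no reaction and one further subject is positive at 15 minutes, then is lost to follow-up. Under Section 10 that subject is dropped and the result is 0/20. Counting the reading gives 1/21 = 4.8%.

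**The case against.** The strongest reply is that nothing is hidden. Section 14 promises every subject's responses in a table, and with 20 to 30 subjects and three readings a reader can count reactors directly. Each subject has one product site, so a positive site nearly amounts to a positive subject. Known fish allergy is excluded and no significant effect is anticipated, so the likely outcome may be zero or one reactor. In those cases the largest interval count equals the number of reactors, provided that all readings are present.

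Much of this stands. It makes the fault one of the planned headline, not of the data. It does not supply a rule for the conclusion: the listing is raw data, and the sentence that governs the conclusion refers to intervals.

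A reader might infer more than the documents support:

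- *That the share of reactors is lost.* It can be derived from the table; it is just not planned as a reported summary.
- *That a persisting wheal is counted three times.* No adding of interval counts is planned, and showing a wheal on every line where it is present is correct.
- *That a subject must be positive at all three readings to count.* This strains the wording. Section 9.6 calls a wheal positive when describing the first reading, with no requirement that it persist.
- *That an any-reading rate can be calculated from a per-reading rate by treating readings as independent.* They are repeat readings of the same prick site in the same person, and the documents give no rates.

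**Conclusion.** The point holds in limited form. The basis for the product conclusion cannot be applied as written, because it requires significance where no analysis is planned. The plan also has no subject-level summary over the three readings. Interval lines can understate the share of reactors when different subjects react at different readings; in the illustration, 5% on every line is compatible with 15% of subjects.

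The size rests on assumed counts, a denominator of 20 and complete readings. If there are no reactors, or the same people react throughout, the discrepancy disappears. It would be wrong to say that the change can only make the product look worse, since step 5 shows movement in both directions. The change is worth making because it settles the headline before results are seen.

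**What to change.** Replace the interval sentence in Section 14 with:

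> The product result is the number of subjects with a positive product site at any of T1, T2 or T3, out of subjects with valid controls and at least one product reading, with an exact 95% confidence interval. The number missing a later reading is stated, and the same result is given for subjects with all three readings. Counts at each interval, and the reading at which each reactor was first positive, are supportive.

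The statement that no statistical analysis will be performed should then be reworded to allow this descriptive summary.

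Reconcile Section 10 with the new sentence so that a positive reading obtained before discontinuation is counted whatever the reason for leaving. The new sentence also relies on one definition of a positive site. Section 7 gives the 3 mm cut-off both as at least 3 mm and as more than 3 mm, and these need to be made consistent.

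The cost is small: one replaced sentence and its consequential rewording in Section 14, two rows in the report table, an edit to Section 10, and approval through the Section 12 amendment route. No new data, visits or measurements are needed.

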## **15. RECORDS RETENTION**

All original samples, raw data sheets, technician's notebooks, correspondence files, a copy of final report and remaining specimens will be maintained on the premises of the clinic in limited access marked storage files. A duplicate copy of the final report will be separately archived at ALS. All records pertaining to this study will be retained by ALS, for a period of not less than six (6) years following the submission of the final report.

**APPENDIX I:**

**QUESTIONNAIRE FOR SUBJECT RECRUITMENT SPT**  
**Study Number: 23-233**

**Subject ID:** \_\_\_\_\_ **Fitz:** \_\_\_\_\_ **Subject Initials:** \_\_\_\_\_  
**Age:** \_\_\_\_\_ **(18-70)** **Date of Birth:** \_\_\_\_\_ **Race:** \_\_\_\_\_ **Sex:** \_\_\_\_\_

Test Site: Inner Forearms	Circle Response	
1. Do you understand that this is a pre-screening recruitment and does not guarantee you will be enrolled on the study? The study is enrolled on a first come first serve basis.	YES	NO
2. Do you have a history of hypersensitivity or allergic reactions to any cosmetics, personal care products, fragrances adhesives and/or a known allergy to fish?	YES	NO
3. Have you used any of the following topical/oral anti-inflammatory medications (i.e. Tylenol, Aspirin, Ibuprofen, Naproxen) or/and anti-histamines and/or immunosuppressive medication, anti-depressants, sedatives, and/or anxiolytics at least 2-weeks prior to the start of the study?	YES	NO
4. Have you participated in any study involving the same test site in the past 30 days?	YES	NO
5. Do you have damaged skin on or in close proximity to test sites (e.g., sunburn, excessive hair, back acne, uneven skin pigmentation, tattoos, scars or other disfigurements)?	YES	NO
6. Do you agree to refrain from swimming, sun bathing and prolonged exposure to sunlight (outdoors) during the length of the study?	YES	NO
7. Have you been diagnosed with any of the following that might interfere with or increase the risk on study participation?		
a. active or chronic skin allergies (atopic dermatitis/eczema)	YES	NO
b. acute or chronic diseases	YES	NO
c. recently treated skin cancer within the last 12 months	YES	NO
d. are you insulin dependent for diabetes?	YES	NO
10. Are you pregnant, or nursing or planning to get pregnant?	YES	NO
10a. For Females ONLY, please list your method of birth control: _____		
11. Do you agree to refrain from using any topical/oral anti-inflammatory medications (i.e., Tylenol, Aspirin, Ibuprofen, Naproxen) or/and anti-histamines and/or immunosuppressive medication during the length of the study (3 Days)?	YES	NO
12. Do you have a history of dermatographism? (also known as dermatographia) is a common, benign skin condition in which even a small amount of pressure, like scratching, causes the skin to swell along the line where it was applied.	YES	NO
13. Do you agree to protect the test site during the length of the study (3 days) from water and/or damage? No cleansing of site allowed.	YES	NO

**Recruited by:** \_\_\_\_\_

**Initials/Date**

**APPENDIX II:**

**23-233 A QUESTIONNAIRE FOR SUBJECT ENROLLMENT**

**Subject ID:** \_\_\_\_\_

**Subject Initials:** \_\_\_\_\_

1) Are you aware that this study involves research? **YES / NO** (circle one)

2) How long is your study participation? \_\_\_\_\_

3) Where will the test product be applied? \_\_\_\_\_

4) How many test sites will be used? \_\_\_\_\_

5) Female volunteers:

Are you pregnant, or nursing or planning to get pregnant? YES / NO / MALE (circle one)

If of child bearing potential, list means of birth control subject agrees to use while participating on study.

\_\_\_\_\_

6) What are some possible side reactions expected from this study? \_\_\_\_\_

7) How many total visits will you make to the facility? \_\_\_\_\_

8) What is the expected duration of the testing visits? \_\_\_\_\_

9) Do you understand the study will require a use of a UniTest PC device on the test sites, which may be painful for individuals?

**YES / NO** (circle one)

10) Do you understand that you will be discontinued from the study without full compensation if you fail to complete all required study visits?

**YES / NO** (circle one)

11) Have all your questions about the study process been answered? **YES / NO** (circle one)

**L:** \_\_\_\_\_ **b\*** \_\_\_\_\_ **Fitzpatrick Score:** \_\_\_\_\_ (I-V)

ALS Staff Initial \_\_\_\_\_ Date \_\_\_\_\_

Subject Initial \_\_\_\_\_ Date \_\_\_\_\_
